Roughly half (47%) had been addicted to amphetamines, one quarter (27%) to alcohol. A fifth had been addicted to opiates and 7% to cannabis. Length of sobriety at baseline was 48 days (SD=32 days). The women had had 6 previous treatment episodes (SD=3). On a 0-10 point scale with high numbers indicating high levels, the women had high commitment to

sobriety (10, SD=1), moderate happiness with recovery (7, SD=2), and moderate confidence in their ability to remain sober (6, SD=2). On a scale that could range from 5-35, their average satisfaction with life was 15 (SD=6). Craving for drugs or alcohol was moderate on a 0-10 point scale: 5 (SD=3).

This study provided preliminary evidence for acceptability and feasibility of PPJ. On a scale of 0-10, with 10 representing high levels, participants gave PPJ high ratings for being easy (8.6), satisfying (8.0), pleasant (7.9), and helpful (8.0) and low ratings for being difficult (1.6).

In the sample overall, there were significant increases in satisfaction with life, happiness with recovery, and confidence in the ability to remain abstinent. Commitment to sobriety did not increase perhaps because baseline average levels were at the top of the scale (9.5/10 points).

In the qualitative data, participants emphasized two main benefits from PPJ: 1) PPJ helped them to realize that more good things than bad things happened in a day and 2) PPJ's right-hand side served as a simple planner which reminded the participants to do things that were important and meaningful to them. When they were reminded in this way, the participants acted to accomplish a wide range of recovery-supportive behaviors.

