Rationale for PPJ. *Why combine daily life review (including gratitude interventions) with planning for the future (activity scheduling) in a daily exercise?* Gratitude interventions and activity scheduling should reinforce and extend each other’s impact. A positive correlation between higher levels of gratitude and greater behavioral activity have been reported.^{29,30} This association may be causal: in previous research, gratitude has been shown to improve affect^{17,31} which has been shown to encourage more frequent and more diverse types of activity.³² Therefore, gratitude intervention should encourage positive, abstinent behavior. Conversely, activity scheduling will enhance gratitude by guiding individuals to shape

their own positive experiences rather than to passively notice them.

Positive behaviors will produce content to populate the next day's gratitude inventory.

3. The next phase of this study will add to the existing knowledge base because we will collect more information about PPJ's feasibility, acceptability and impact with a larger sample size. Our development study included only women; this phase of the study will include women and men. We will also have a control group in this next phase of the study. We will also modify the protocol so we can conduct the study on Zoom to comply with shelter-in-place orders and COVID19 best practices Study Endpoints/Events/Outcomes

- 3.1. Primary Endpoint/Event/Outcome: The primary outcome is empirical data on the feasibility and acceptability of PPJ. We will also assess rates of substance use and treatment retention as primary outcomes.
- 3.2. Secondary Endpoint(s)/Event(s)/Outcome(s): These include hypothesized mediators of the effect of the intervention on outcomes. These include: mood, satisfaction with life, commitment to sobriety, alcohol and drug craving, anxiety, and depression. For a complete list, see the measures section 5.2.

4. Study Intervention(s)/Interaction(s)

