Secondary measures: outcomes and mediators. We will compare rates of treatment retention and recurrence of substance use to the general rates reported by NUWAY. We will also examine pre-post treatment means and standard deviations of hypothesized mediators (affect, satisfaction with recovery, individual items theoretically related to PPJ) to determine if change is in the expected direction. We will also study these constructs to determine if there is reasonable variability in the data we collect or if floor or ceiling effects are present. We may also use single-subject designs⁵⁶ to depict change over time in key constructs by study participant. Qualitative data will be thematically analyzed using the techniques recommended by Braun and Clarke.¹³ Here, the researcher examines transcripts of texts and identifies key themes and how themes relate to one another. These data will inform intervention development and study implementation procedures.

Data analytic techniques to compare treatment and control groups. While this pilot study will not be adequately powered to detect significant effects between treatment and control groups, we will compare differences between the treatment and control groups at baseline and over time using either t-tests or multi-level modeling. T-tests will reveal significant differences between groups and multi-level modeling will show whether rate of change is significantly different between groups.

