“in the last week” would mean in the week that ends today. Please know I will not be asking you any follow up questions for any of these next questions. Depending on some of your answers, I might need to let NUWAY staff know of your replies.” We would consider a high score to be two or more past-week symptoms for each subscale: internalizing disorder, externalizing disorder, or criminal/violent behavior. Exclusion from the study based on these items would include endorsing “last week” for certain items such as: “thinking about ending your life or committing suicide,” “lied or conned to get things you wanted or to avoid having to do something,” having a hard time “paying attention at school/work/home” in combination with having a hard time “listening to instructions at school/work/home,” “were a bully or threatened other people,” “started physical fights with other people,” “had a disagreement in which you pushed, grabbed, or shoved someone,” and “purposely damaged or destroyed property that did not belong to you.” In the event of high scores in any of the three subscales or a single score of “last week” for any of these selected items, the person would not be eligible for the study. However, in each of these cases, we would discuss the results with NUWAY staff before determining final eligibility for the study.

8. The requirement of 2 weeks continuous sobriety before enrollment in the study may be waved based on clinical judgment.
9. Participant would read/review/discuss with study staff the informed consent/HIPAA consent combined document. Participant would read/review/discuss with study staff the HIPAA consent document.
10. Research staff would ask the participant the questions from the UBACC quiz to determine capacity to consent.⁵⁷ A score of 15 or higher is needed for inclusion in the study. The prospective participant can review the study details and return to re-do the quiz another day if this is possible given the study timeline.
11. If they score over 15 on the UBACC and meet all other study inclusion/exclusion criteria, or if they are eligible for the wait list, they will sign the main informed consent document (electronically if electronic administration). These forms will be signed in duplicate, providing one copy for research staff and one for participant (duplication unnecessary for electronic administration).
12. If the participant is deemed to meet all study criteria, they would move on to take the baseline assessment instrument.

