"We will not ask you about child or vulnerable adult abuse. If you tell us about child or vulnerable adult abuse or neglect, we may have to report it to authorities because of law or policy. This is true if you tell us in group, one on one meetings, or in journal entries. Also, if we learn (in person or in any other contact you have with us) that you are at risk for hurting yourself or others, we will inform NUWAY treatment staff of this information as soon as possible.

"In general, if something worries us about what you share with us in any way, we will let NUWAY staff know. This includes any time you tell us that you have used drugs or alcohol. Telling us that you have used drugs or alcohol will have the same consequences as if you told a NUWAY staff member that you used drugs or alcohol. NUWAY staff would work with you to make sure that you have the support you need to get back on track related to your recovery.

"If you tell us that you committed a crime, we would tell NUWAY Staff. Telling us that you committed a crime would have the same consequences as if you told a NUWAY staff member that you committed a crime. If you are on probation or parole, NUWAY staff would need to report this to your probation or parole officer.

"If you tell us that you intend to hurt yourself or someone else, we would tell NUWAY staff.

"Some of these things that you might tell us might have consequences related to your treatment status at NUWAY.

"In general, the NUWAY Staff will not find out your answers to the iPad surveys."

11. Number of Participants

11.1. Number of participants to be consented will be approximately 100.

12. Recruitment Methods

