Interested clients will contact research study staff by phone, email, or text. Whenever possible, study staff will conduct a preliminary screening and if the participant appears eligible, make an appointment for the screening interview. When a preliminary screening is not possible, the preliminary screening questions will be the first questions asked at the screening interview. The preliminary screening questions are designed to determine as quickly as possible when a person might be eligible for the study and will be conducted via a brief telephone call. The preliminary screening questions are as follows: 1. Are you now a client at NUWAY? 2. How long have you been a client at NUWAY? (6 day minimum is required). 3. What is

your latest date of sobriety? (6 day minimum is required). 4. Are you at least 18 years old? 5. Who is your counselor and what NUWAY facility are you attending? 6. If you are part of this study, you might be asked to join a zoom group that meets from [insert time of group, e.g., 12 to 1 pm] on 8 weekdays, starting [insert start date]. Would that work for your schedule? 7. If you are part of this study, we'll be contacting you by email regularly. Would you be willing to check your email daily? 8. How is your ability to read and write in English? 9. Do you have a device (smartphone/tablet) that has a camera in it, and can connect to the internet? Would you be willing to use this device for the research study? 10. Are you able to attend Zoom meetings for the research study? 11. Are you able to fill out electronic questionnaires that we will send to you? 12. What questions can we answer about the research study?

At the screening interview, research staff will guide prospective participants through the screening informed consent, regular informed consent procedure, take the baseline questionnaire, and be randomized into the treatment (maroon) or control (gold) groups. Individuals who meet criteria for the waiting list would also have the opportunity to take the baseline screening instrument.

12.2. Source of Participants: All participants to be enrolled in the study will be concurrently receiving SUD treatment at NUWAY Inc. Study participation is offered in addition to SUD treatment as usual, but participants may miss NUWAY groups in order to instead attend PPJ groups. This decision will be made by NUWAY staff. During COVID19, our groups will be offered at times other than NUWAY core remote treatment groups whenever possible.

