17.2. Power Analysis: Preliminary data from existing behavioral activation (BA) research was used to determine power for the original proposal with N=76. For the outcome of abstinence (yes/no), previous work found outcomes for this variable of 41.5% for the BA group and 24.8% in the control group.¹⁴ For a 1-tailed test with $p < .10$, our power to detect a significant effect for abstinence (yes/no) in the proposed study would be .61 (for a 2-tailed test with $p < .05$, power would be .34). For the outcome of treatment retention (yes/no), previous work showed 96.6% for the BA group and 75.9% in the control group.¹⁶ For a 1-tailed test with $p < .10$, our power to detect a significant effect for treatment retention (yes/no) in the current study would be 94% (for a 2-tailed test with $p < .05$, power would be .82). Therefore, we should be adequately powered to detect statistically significant differences for the outcome of treatment retention in the current study using a 2-tailed test. R was used to conduct these power analyses.⁶¹

17.3. Statistical Analysis: This pilot study will not be adequately powered to detect an effect. Still we will compare the treatment and control groups using t tests and multi-level models to determine differences in means and in slopes between the groups, respectively. Descriptive statistics of the quantitative measures will be used to conduct power analyses and sample size calculations for a larger controlled trial. Also, multi-level analyses will

be conducted to determine significant change over time in factors of interest. We will also be able to examine whether change over time varied by certain subgroups (e.g., those with lower versus higher levels of the factor of interest at baseline).

17.4. Data Integrity: The use of Qualtrics to collect survey data will improve data accuracy because this allows us to avoid keystroke and other errors involved with manual data entry from written questionnaires. We will scrutinize the data produced by Qualtrics to ensure its integrity; whether values are within scale ranges and whether missing data is coded correctly. We will carefully examine and clean the data to ensure accuracy. For standardized instruments, we will be very careful to follow the directions for summing or taking the mean of scale items and reverse code any items as per the instructions.

18. Confidentiality

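### Time sober and time since NUWAY admission are known before randomisation, but no planned arm comparison of recurrence or retention uses them; adjusting may recover some precision at almost no cost

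*Combined protocol and SAP*

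**What the plan says.** - **Outcomes.** Section 3.1 puts recurrence and retention among the primary outcomes: "We will also assess rates of substance use and treatment retention as primary outcomes". The Analysis Plan in 5.2 lists them under secondary measures.
- **Baseline information.** The preliminary screening questions in 12.1 ask "How long have you been a client at NUWAY? (6 day minimum is required") and "your latest date of sobriety? (6 day minimum is required"). Section 5.4 makes NUWAY staff and records the back-up for the entry date. Section 5.2 places randomisation after screening and the baseline battery, and names no stratification factor.
- **Spread at entry.** Section 2.2 gives one figure, from phase 1: "Length of sobriety at baseline was 48 days (SD=32 days"). Section 9.1 asks for about two weeks of abstinence and of treatment, while 12.1 uses six days; this point does not depend on which applies. Section 9.3 item 8 adds "The requirement of 2 weeks continuous sobriety before enrollment in the study may be waved based on clinical judgment".
- **Arm comparison.** Section 5.2: "we will compare differences between the treatment and control groups at baseline and over time using either t-tests or multi-level modeling". Section 17.3 repeats this without covariates. Its one use of baseline values is to ask whether change over time differs by subgroup. The only analysis written specifically for recurrence and retention compares them with NUWAY's general rates.
- **Power.** Section 17.2 treats both outcomes as two simple proportions; prior research "was used to determine power for the original proposal with N=76". Section 11.1 now says "Number of participants to be consented will be approximately 100".

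**The concern.** Recurrence and retention are yes/no outcomes with no baseline score of their own, so a baseline adjustment has to come from another variable. Time sober and time in treatment are natural candidates. The entry rules set a minimum on each. Retention is scored by how the person leaves a programme that 23.1 says generally lasts 90-120 days, while 8.1 has each participant in the study for five to nine weeks. Someone randomised on day 80 of treatment can finish within nine weeks (80 + 63 = 143 days). Someone randomised on day 7 generally cannot (7 + 63 = 70 days).

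If these variables matter, a chance difference between arms passes straight into the crude difference in rates. Section 17.3 intends the pilot's descriptive results to size a larger trial, so such a shift could carry forward. Naming the covariates in advance also rules out choosing them after the planned baseline comparison has been seen.

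**Working it through.** **Inputs from the documents.** Abstinence 41.5% v 24.8%; retention 96.6% v 75.9%; N=76 for the power figures (17.2); about 100 to be consented (11.1); SD of days sober 32 (2.2, phase 1).

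**Assumptions.** Allocation 1:1, so 38 or 50 per arm. No dropout. Strength of the covariate: odds ratio 1.0 to 3.0 per SD, because the documents give none.

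**Step 1: reproduce 17.2.** Arcsine effect size h = 2·asin√p₁ − 2·asin√p₂; power = Φ(h√(n/2) − z).

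- Abstinence: h = 0.357; h√19 = 1.558; power .344 (two-sided .05) and .609 (one-sided .10). Stated: .34 and .61.
- Retention: h = 0.655; h√19 = 2.857; power .815 and .942. Stated: .82 and .94.

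The stated figures reproduce, and they are unadjusted. At 50 per arm, two-sided power becomes .431 for abstinence and .906 for retention.

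**Step 2: chance imbalance in days sober, if SD = 32 applies.** SE = 32·√(2/n).

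| Per arm | SE (days) | 95% range | P(gap > 10 days) |
|---|---|---|---|
| 38 | 7.3 | ±14.4 | 17% |
| 50 | 6.4 | ±12.5 | 12% |

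At 50 per arm, a gap of 1.96 SE is 1.96 × √(2/50) = 0.39 SD. Averaging the logistic curve over a normal covariate, with marginal rates between 24.8% and 41.5%, that gap moves the crude difference by about 3-4, 5-6 or 7-8 points for odds ratios of 1.5, 2 or 3. The planning effect is 41.5 − 24.8 = 16.7 points. A gap of that size or larger is a 1-in-20 event.

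**Step 3: power with and without one covariate.** Simulation with 4,000 trials per cell, a single standardised covariate, marginal rates held at the stated values, and a two-sided 5% likelihood-ratio test.

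| Odds ratio per SD | Abstinence, N=100: unadjusted → adjusted | Retention, N=76: unadjusted → adjusted |
|---|---|---|
| 1.0 | .408 → .420 | .832 → .834 |
| 1.5 | .424 → .444 | .830 → .836 |
| 2.0 | .427 → .476 | .805 → .826 |
| 3.0 | .428 → .521 | .828 → .865 |

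The Monte Carlo standard error of one abstinence figure is √(.43 × .57/4000) = .008. The 1.2-point rise at odds ratio 1.0 is not information gained; it reflects noise and slight liberality of the test in small samples. The 2-point rise at 1.5 should be discounted accordingly. A second simulation of 1,500 trials per cell gave retention gains of 0.5 to 3.3 points (.813/.818, .833/.856, .828/.861).

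**Step 4: a rougher check.** Scaling the variance by (1 − R²) in the Step 1 formula takes abstinence at N=100 from .431 to .450, .470 and .515 for R² of .05, .10 and .20. Retention at N=76 goes from .815 to .834, .853 and .891. For retention this shortcut is more optimistic than the simulation, where odds ratio 3 corresponds to R² of about .14.

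**Step 5: retention failures available to a model.** N=76: 38 × .034 + 38 × .241 = 10.5. N=100: 50 × .034 + 50 × .241 = 13.8. That is about 10 to 14 in total, which supports very few covariates.

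**The case against.** **Harm not shown.** Nothing in the documents ties either variable to recurrence or retention. Sections 14.1 and 19.2 relate time in treatment to being past acute withdrawal, which is a threshold and not a gradient above it. Sections 9.1 and 9.3 favour clients who will stay for the whole study, which may narrow the spread in time left. This stands: the loss is conditional.

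**The SD may not transfer.** It comes from 15 women in the one-arm phase, at a host site that 5.2 describes as residential. The trial takes men and women, mainly outpatients. This stands: 32 days shows that spread can be wide and no more.

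**The simulation is not the retention model.** It used one generic covariate standing for days sober. Days since admission has no SD in the documents and was not modelled. This stands.

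**Other covariates could be chosen.** Addiction severity, craving, commitment and self-efficacy are also measured at baseline. True, but recording both dates is already part of screening, and days since admission bears on how retention is scored.

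**A pilot's conclusions would not change.** Feasibility is the main objective, and 5.2 and 17.3 concede low power. No binary-outcome method is stated at all, which is a larger gap. This limits the importance of the point, but the same few sentences would fill that gap.

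**Stronger readings to avoid.** A reader might infer that the unadjusted comparison is biased or invalid. It is not: randomisation protects it, and its error rate already allows for chance imbalance. A reader might also infer that precision is certainly lost, or that adjustment would make the trial adequately powered for abstinence. The documents support neither; the highest simulated figure is .52.

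**Conclusion.** Both variables are available before randomisation, and no comparison of recurrence or retention is planned to use them. This is a missed, nearly free improvement and not an error of validity. For abstinence at N=100 the power gain is about 2 to 9 points under assumed odds ratios of 1.5 to 3, part of the smallest being artefact, and nil without an association. For retention at N=76 it is about 0 to 3 points, 3.7 in the highest simulated cell. These sizes rest on 1:1 allocation, no dropout, the rates in 17.2 and an assumed strength of association. The imbalance in days further assumes that the phase 1 SD carries over.

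**What to change.** In 5.2 and 17.3, state that:

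- arms are compared on recurrence by logistic regression with arm and log(days since last use), and on retention with arm and log(days since NUWAY admission), each continuous and calculated at randomisation;
- retention is fitted by penalised likelihood from the outset, because only about 10 to 14 failures are expected, with no switch of model that depends on the data;
- the standardised risk difference with 95% CI is reported for each outcome beside the crude rates;
- the last-use date and the NUWAY entry date are kept in the analysis data set, since neither is listed by name in Table 2 or among the baseline measures.

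The cost is a few sentences and slightly more analysis, with no new data collection. The downside is slight model dependence when events are sparse, which one fixed covariate per outcome keeps small.
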